5.3. Lifestyle Considerations

Male and female subjects of reproductive potential (i.e., not surgically sterile or female subjects who are not postmenopausal) must use highly effective contraception for the duration of the study interventions and for at least 4 months after the last dose of study interventions. Please see Section 10.4 for detailed contraceptive requirements.

Subjects should be advised to use appropriate protective measures to minimize exposure to direct sunlight or UV light sources during the treatment period and for at least 30 days after the last dose of duvelisib. Please see the duvelisib IB for additional details on the potential for phototoxicity.

Subjects should refrain from consumption of grapefruit juice and St. John's Wort, and other foods and herbal products that are strong inhibitors or inducers of CYP3A during treatment with duvelisib. Please see Section 6.5.2 for additional information on restrictions on the use of CYP 3A inhibitors, inducers, and substrates, and Section 10.2 for lists of CYP3A inhibitors, inducers, and substrates. The duvelisib IB contains additional details on potential interactions with foods.

5.4. Definition of Enrolled

“Enrolled” means a subject's, or their legally acceptable representative's, agreement to participate in a clinical study after completion of the informed consent process. Potential subjects who are pre-screened for the purpose of determining eligibility for the study but do not sign an ICF are not considered enrolled.

5.5. Screen Failures

Screen failures are defined as subjects who consent to participate in the clinical study but are not subsequently assigned to study intervention. A minimal set of screen failure information is required to ensure transparent reporting of screen failure subjects to meet the Consolidated Standards of Reporting Trials publishing requirements and to respond to queries from regulatory authorities. Minimal information includes demography, screen failure details, eligibility criteria, and any SAEs that occur after the ICF is signed.

Individuals who do not meet the criteria for participation in this study (screen failure) may be rescreened. A subject who is rescreened is not required to sign another ICF if the rescreening occurs within 30 days from the previous ICF signature date. Please note that repeating of clinical laboratory assessments during screening does not constitute rescreening.

5.6. Replacement of Subjects

During the DLT evaluation period in Stage 1, subjects who discontinue duvelisib before the end of Cycle 1, for reasons other than a DLT, or who receive < 75% of the scheduled duvelisib doses during Cycle 1 may be replaced.

Any other subjects who withdraw from the study for reasons other than PD or treatment-related toxicity before receiving at least 1 cycle of study intervention may be replaced.

6. STUDY INTERVENTIONS

Study intervention(s) is defined as any investigational intervention(s), marketed product(s), placebo, or medical device(s) intended to be administered to a study subject according to the study protocol.

6.1. Study Interventions Administered

Table 7: Study Interventions

Intervention Name	Duvelisib	Pembrolizumab
Type	Investigational Drug	Biologic
Drug Substance Description	White to off-white crystalline solid	Sterile, preservative-free, non-pyrogenic, clear to slightly opalescent, colorless to slightly yellow solution
Dose Formulation	Capsule	Vial
Unit Dose Strength(s)	15 mg, 25 mg	100 mg/4 mL
Formulation Excipients	Excipients (diluent, glidant, disintegrant, and lubricant) that are listed in the US FDA Inactive Ingredients Database for approved drug products and/or GRAS	L-histidine (1.55 mg), polysorbate 80 (0.2 mg), sucrose (70 mg), and Water for Injection, USP
Dosage Level(s) and Frequency^a	25 mg PO BID	200 mg IV q3w
Route of Administration	Oral	IV
Use	Experimental	Experimental
IMP or NIMP	IMP	NIMP
Sourcing	Provided by the Sponsor	Site Pharmacy
Packaging and Labeling	Prepared to meet all regulatory requirements	As described in Keytruda® US prescribing information
Current/Former Name(s) or Alias(es)	VS-0145, IPI-145, Copiktra®	Keytruda®

Abbreviations: BID: twice daily; FDA: Food and Drug Administration; GRAS: Generally Regarded as Safe; IMP: Investigational Medicinal Product; IV: intravenous; NIMP: Non-Investigational Medicinal Product; PO: oral; q3w: every 3 weeks; US: United States; USP: United States Pharmacopeia.

^a Subjects will be treated until documented PD (Section 8.1.2), unacceptable toxicity (Section 6.7), discontinuation criteria are met, withdrawal (Section 7.2), or death. The total duration of treatment will not exceed 24 months.

6.1.1. Duvelisib

Duvelisib should be swallowed whole with a glass of water (approximately 8 ounces or 240 mL). Advise subjects not to open, break, or chew the capsules.

Duvelisib 25 mg will be administered BID PO. Duvelisib may be administered without regard to meals; however, subjects must avoid grapefruit and grapefruit juice while on duvelisib ([COPIKTRA 2018](#)).

On days of pembrolizumab dosing, duvelisib will be administered in the clinic before the pembrolizumab infusion is started.

On the days when postdose PK samples are collected, specific timing for the administration of duvelisib is required (see [Table 2](#) and [Table 4](#)), as follows:

- Stage 1: On C1D8, duvelisib will be administered at the start of the visit after the predose PK, pharmacodynamic, and blood sample collection
- Stage 1: On C2D1, duvelisib will be administered 30 minutes before the start of the pembrolizumab infusion
- Stage 2: On C1D1, duvelisib will be administered at the start of the visit after the predose PK and blood sample collection

Refer to the Pharmacy Manual for additional instructions regarding duvelisib administration.

6.1.2. Pembrolizumab

Pembrolizumab will only be administered by qualified site personnel during clinic visits in accordance with the prescribing information for pembrolizumab ([Keytruda 2019](#)).

Pembrolizumab 200 mg should be administered q3w as an IV infusion over 30 minutes.

On the days when postdose PK samples are collected, specific timing for the administration of pembrolizumab is required (see [Table 2](#) and [Table 4](#)) as follows:

- Stage 1: On C1D8, pembrolizumab will not be administered until the biopsy for biomarkers has been collected; the optimal timing for collection of the biopsy is approximately 2 to 4 hours after duvelisib administration, however, a tumor biopsy at a later time during this clinic visit on C1D8 is acceptable. The fourth PK sample should be collected at approximately 2 to 4 hours after duvelisib dose, as soon as possible after the biopsy, and prior to pembrolizumab administration.
- Stage 1: On C2D1, the pembrolizumab infusion will be started 30 minutes after administration of duvelisib
- Stage 2: On C1D1, pembrolizumab will be administered 30 minutes after collection of the 2-hour postdose duvelisib PK sample

With the exception of the days when postdose PK samples are collected (i.e., C1D8 and C2D1 in Stage 1 and C1D1 in Stage 2), the pembrolizumab infusion should be started within 10 minutes after the dose of duvelisib is administered.

Please refer to the prescribing information for current detailed instructions on administration of pembrolizumab ([Keytruda 2019](#)).

6.2. Preparation/Handling/Storage

6.2.1. Duvelisib

Dispensing and storage instructions for duvelisib will be provided in the Pharmacy Manual. On receipt at the investigative site, duvelisib should remain in the packaging as provided until use or dispensation. The packaged product should be stored at the investigative site at 20 to 25°C (68 to 77°F), with excursions permitted at 15 to 30°C (59 to 86°F). Temperature excursion procedures are provided in the Pharmacy Manual. Expired drug is not to be dispensed ([COPIKTRA 2018](#)).

6.2.2. Pembrolizumab

Please refer to the prescribing information for current instructions on preparation, handling, and storage of pembrolizumab ([Keytruda 2019](#)).

Pembrolizumab to be used in combination with duvelisib in this study will be obtained by the study sites from commercially available sources.

6.2.3. Accountability

Only subjects enrolled in the study may receive study interventions (i.e., duvelisib in combination with pembrolizumab) and only authorized site staff may supply or administer study interventions.

All study interventions stored at the site must be stored in a secure, environmentally-controlled, and monitored (manual or automated) area in accordance with the labeled storage conditions with access limited to the Investigator and authorized site staff.

The Investigator, institution, or the head of the medical institution (where applicable) is responsible for study intervention(s) accountability, reconciliation, and record maintenance (i.e., receipt, reconciliation, and final disposition records).

Further guidance and information for the final disposition of unused duvelisib are provided in the Pharmacy Manual.

6.3. Measures to Minimize Bias

This is an open-label study with a single treatment arm.

Subjects will be assigned a unique number in ascending numerical order at each study site.

6.4. Study Intervention Compliance

When subjects are dosed at the site, they will receive study interventions (i.e., duvelisib and pembrolizumab) directly from the Investigator or designee, under medical supervision. The date and time of each dose administered in the clinic will be recorded in the source documents and recorded in the case report form (CRF). The dose of study interventions and study subject identification will be confirmed at the time of dosing by a member of the study site staff.

When subjects administer duvelisib at home, compliance with duvelisib will be assessed by the study site at each visit. Compliance of duvelisib dosing will be assessed by reviewing subject diaries (first year on treatment only) and counting returned capsules during the site visits and will

be documented in the source documents and CRF. Deviation(s) from the prescribed dosage regimen should be recorded in the CRF.

A record of the number of duvelisib capsules dispensed to and taken by each subject must be maintained and reconciled with duvelisib and compliance records. Pembrolizumab infusion start and stop times and duvelisib start and stop dates, including dates for intervention delays and/or dose reductions will also be recorded in the CRF.

6.5. Concomitant Therapy

Any other medication (e.g., supportive care) that is considered necessary for the subject's welfare and that is not expected to interfere with the evaluation of duvelisib may be given at the discretion of the Investigator.

Any medication that the subject received within 30 days prior to the first dose or receives during the study must be recorded along with:

- Reason for use
- Dates of administration including start and stop dates
- Dosage information including dose and frequency

The Medical Monitor should be contacted if there are any questions regarding concomitant or prior therapy.

6.5.1. Required and Recommended Prophylaxis

Based on the duvelisib clinical experience to date, the following are required or recommended:

- Subjects are required to receive pneumocystis prophylaxis concomitant with duvelisib treatment per institutional guidelines. After completion/discontinuation of duvelisib treatment, continue prophylaxis until the absolute CD4+ T-cell count is greater than 200 cells/ μ L.
- HSV and VZV infections have been observed with duvelisib; therefore, herpes (HSV/VZV) prophylaxis concomitant with treatment is recommended, per Investigator discretion according to institutional guidelines
- Subjects with a history of CMV infection/reactivation or viremia should be monitored for reactivation by polymerase chain reaction (PCR) or antigen test at least monthly. Prophylactic treatment per institutional guidelines is recommended for subjects considered by Investigators to be at high risk for CMV reactivation.
- Antimicrobial prophylaxis and pneumococcal pneumonia vaccine are recommended for subjects with history of or considered at high risk for infections and during periods of severe neutropenia. Choice of antimicrobial agent (antifungal, antibiotic, antiviral) is per Investigator discretion, but the restrictions on the use of CYP3A inducers, inhibitors, and substrates should be considered (see Section [6.5.2](#)).

6.5.2. Concomitant Therapies Restrictions**Table 8: Prohibited Concomitant Therapies**

Prohibited Concomitant Therapy	Guidance
Use of Vaccines	
For all subjects, the use of live or live attenuated vaccines is prohibited during the treatment with either study intervention.
 
The use of inactivated (or killed) vaccines (such as pneumococcal pneumonia vaccine) is allowed during the study; however, subjects and their physicians should be aware that the effectiveness of any vaccine administered concomitantly with duvelisib may be diminished. The ability to generate an immune response to any vaccine after the administration of duvelisib has not been studied and data for pembrolizumab are preliminary (Läubli 2018).

Immunosuppressants	
Subjects are not to receive ongoing treatment with chronic immunosuppressants (e.g., cyclosporine) or systemic steroids for > 1 week at doses higher than the equivalent of 20 mg prednisone QD.
 
Note: Acute treatment for underlying autoimmune disorders (e.g., reactive airway disease, rheumatoid arthritis) with corticosteroid doses > 20 mg prednisone or equivalent QD for \leq 1 week is permitted during the study. Corticosteroid doses of \leq 20 mg prednisone or equivalent QD are permitted during the study for physiologic replacement or chronic treatment for underlying autoimmune disorders (e.g., reactive airway disease, rheumatoid arthritis).
 
See Table 10 and Table 13 for use of systemic steroids for study intervention toxicity when study intervention(s) is withheld or discontinued.

Other Anticancer Therapy or Investigational Agents	
During the study intervention period, subjects are not to receive any additional anticancer therapy or other investigational agents not outlined in the protocol.

Medications or Foods that Strongly Inhibit or Induce CYP3A4	
Use of a strong CYP3A inhibitor or inducer during treatment with duvelisib is prohibited. Co-administration with a strong CYP3A inhibitor increases duvelisib exposure, which may increase the risk of duvelisib toxicities. Co-administration with a strong CYP3A inducer decreases duvelisib exposure, which may reduce duvelisib efficacy.
 
Section 10.2 provides a list of medications and foods known to inhibit (Table 20) or induce (Table 21) CYP3A. Please note that these tables do not provide a comprehensive list of all medications that may modulate CYP3A activity.
 
No formal PK drug-drug interaction studies have been conducted with pembrolizumab (Keytruda 2019).

Abbreviations: CYP3A: cytochrome P450 3A; QD: once daily; PK: pharmacokinetic.

Table 9: Concomitant Therapies: Use with Caution During Treatment with Duvelisib

Concomitant Therapy: Use with Caution	Guidance
Medications or Foods that Weakly or Moderately Inhibit or Induce CYP3A4	Please discuss use of weak or moderate CYP3A inhibitors and inducers with the Medical Monitor. Section 10.2 provides a list of medications and foods known to inhibit (Table 20) or induce (Table 21) CYP3A. Please note that these tables do not provide a comprehensive list of all medications that may modulate CYP3A activity.
Medications that are Substrates of CYP3A	Co-administration with duvelisib decreases AUC of a sensitive CYP3A4 substrate which may decrease the efficacy of these drugs. Consider finding an alternative drug that is not a substrate of CYP3A4. Table 22 in Section 10.2 provides a list of medications known to be substrates of CYP3A. Please note that Table 22 is not a comprehensive list of all medications that may be substrates of CYP3A. The Sponsor should be contacted with any questions regarding concomitant use of medications that are CYP3A substrates.

Abbreviations: AUC: area under the curve; CYP3A: cytochrome P450 3A; QD: once daily.

6.5.3. Contraception and Pregnancy

The effects of duvelisib on conception, pregnancy, and lactation are unknown.

Refer to the prescribing information for pembrolizumab for the effects of pembrolizumab on conception, pregnancy, and lactation (Keytruda 2019).

At Screening, all male and female subjects of reproductive potential (i.e., not surgically sterile or female subjects who are not postmenopausal) must agree to use a highly effective method of contraception for the duration of the study interventions and for at least 4 months after the last dose of study interventions. See Section 10.4 for Contraceptive Guidance including examples of highly effective contraceptive methods. Pregnancy testing will be performed throughout the study as shown in the SoA (Table 1 and Table 3).

6.6. Supportive Care, Dose Modifications, and Management of Toxicities

Supportive care should be provided as clinically indicated. Granulocyte colony stimulating factor may be used according to the American Society of Clinical Oncology (ASCO) guidelines (Smith 2015). Transfusions may be used at any time as clinically indicated and according to ASCO guidelines. Subjects on a stable dose of erythropoietin to treat baseline anemia may continue this therapy at this dose.

General recommendations for the management of overlapping toxicities for duvelisib in combination with pembrolizumab (Section 6.6.1), toxicities for duvelisib (non-overlapping toxicities or as monotherapy) (Section 6.6.2), and toxicities for pembrolizumab (non-overlapping toxicities) (Section 6.6.3) are provided below.

Please refer to the pembrolizumab prescribing information (Keytruda 2019) for additional information regarding management of pembrolizumab toxicities.

Additional information regarding management of duvelisib toxicities can be found in the Summary of Data and Guidance to the Investigator section of the duvelisib IB.

In the event that all study interventions are discontinued, subjects should be followed for AEs (for 30 days after the last dose of last study intervention) and survival as outlined in the SoA ([Table 1](#) and [Table 3](#)).

6.6.1. Recommended Dose Modifications for the Management of Overlapping Toxicities for Duvelisib in Combination with Pembrolizumab

Non-infectious diarrhea or colitis, cutaneous reactions, pneumonitis without suspected infectious cause), and elevations in ALT and AST levels are potential overlapping toxicities for duvelisib with pembrolizumab. Refer to [Table 10](#) for recommended management of these events in subjects being treated with duvelisib in combination with pembrolizumab.

If, during the management of an AE for an individual subject receiving both duvelisib and pembrolizumab, the Investigator suspects that pembrolizumab may be the cause of that event, the Investigator should discuss the case with the Medical Monitor. If an excessive rate of Grade 3 or higher overlapping SAEs is observed, the totality of safety data will be evaluated by the Medical Monitor and the Investigators, and a decision to hold enrollment of subjects may be made (see [Section 4.1](#)).

For additional information, please refer to the prescribing information for pembrolizumab ([Keytruda 2019](#)) and the Summary of Data and Guidance to the Investigator section of the duvelisib IB.

Table 10: Recommended Dose Modifications for the Management of Overlapping Toxicities for Duvelisib in Combination with Pembrolizumab

Toxicity	Adverse Reaction Grade	During Treatment with Duvelisib in Combination with Pembrolizumab	
		Dose Modification	Recommended Management
Non-infectious Diarrhea or colitis	Grade 1 diarrhea (up to 3 stools per day over baseline) and responsive to antidiarrheal agents, OR Asymptomatic (Grade 1) colitis	
 • No change in pembrolizumab dose • No change in duvelisib dose 	
 • Initiate supportive therapy with antidiarrheal agents as appropriate • Monitor at least weekly until resolved or Grade 0
	Grade 1 diarrhea (up to 3 stools per day over baseline) and unresponsive to antidiarrheal agents	
 • Withhold duvelisib dose • No change in pembrolizumab dose 	
 • Treat with enteric acting steroids (e.g., budesonide) • Monitor at least weekly until resolved • Resume duvelisib at a reduced dose when event resolves (see Table 11)
	Grade 2 diarrhea or colitis	
 • Withhold pembrolizumab and duvelisib 	
 • Administer corticosteroids (initial dose of 1 to 2 mg/kg/day prednisone or equivalent followed by a taper) • Resume in subjects with complete or partial resolution (Grades 0 to 1) after corticosteroid taper
	Abdominal pain, stool with mucus or blood, change in bowel habits, peritoneal signs OR Severe diarrhea or colitis (Grade 3, > 6 stools per day over baseline)	
 • Withhold pembrolizumab and duvelisib 	
 • For Grade 2/Grade 3 colitis, initiate supportive therapy with enteric acting steroids (e.g., budesonide) or systemic steroids (initial dose of 1 to 2 mg/kg/day prednisone or equivalent followed by a taper) • Monitor at least weekly until resolved • Resume pembrolizumab treatment when event resolves • Resume duvelisib at a reduced dose when event resolves (see Table 11) • For recurrent Grade 3 diarrhea or recurrent colitis of any grade, discontinue pembrolizumab and duvelisib
	Life-threatening	
 • Discontinue pembrolizumab and duvelisib 	

Toxicity	Adverse Reaction Grade	During Treatment with Duvelisib in Combination with Pembrolizumab	
		Dose Modification	Recommended Management
Cutaneous reactions	Grade 1-2	
 No change in dose for pembrolizumab or duvelisib 	
 Initiate supportive care with emollients, anti-histamines (for pruritus), or topical steroids Monitor closely
	Grade 3	
 Withhold duvelisib dose Based on the severity of the adverse reaction, withhold or permanently discontinue pembrolizumab 	
 Initiate supportive care with emollients, antihistamines (for pruritus), or topical steroids Monitor at least weekly until resolved Resume duvelisib at reduced dose when event resolves (see Table 11) If severe cutaneous reaction does not improve, worsens, or recurs, discontinue duvelisib
	Life-threatening	
 Discontinue pembrolizumab and duvelisib 	
	SJS, TEN, DRESS (any grade)	
 Discontinue pembrolizumab and duvelisib 	
Pneumonitis without suspected infectious cause	Moderate (Grade 2) symptomatic pneumonitis	
 Withhold pembrolizumab and duvelisib 	
 Treat with corticosteroids (1 to 2 mg/kg/day prednisone or equivalent, followed by corticosteroid taper) If pneumonitis recovers to Grade 0 or 1, pembrolizumab may be resumed and duvelisib may be resumed at reduced dose (see Table 11) If non-infectious pneumonitis recurs or subject does not respond to steroid therapy, discontinue duvelisib and pembrolizumab
	Recurrent Grade 2 pneumonitis, severe (Grade 3), or life-threatening pneumonitis	
 Discontinue pembrolizumab and duvelisib 	

Toxicity	Adverse Reaction Grade	During Treatment with Duvelisib in Combination with Pembrolizumab	
		Dose Modification	Recommended Management
Hepatotoxicity	AST or ALT > 3 and up to 5 × ULN or total bilirubin > 1.5 and up to 3 × the ULN	
 Withhold pembrolizumab and duvelisib 	
 Treat with corticosteroids (0.5 to 1 mg/kg/day prednisone or equivalent followed by corticosteroid taper) Monitor at least weekly until ALT or AST returns to < 3 × ULN Resume treatment when adverse reaction improves to Grade 0 or 1 after corticosteroid taper
	In subjects without liver metastases, AST or ALT > 5 × ULN or total bilirubin > 3 × ULN	
 Discontinue pembrolizumab and duvelisib 	
	In subjects with liver metastasis and Grade 2 AST or ALT at baseline, with an increase in AST or ALT of 50% or more relative to baseline that persists for at least 1 week	
 Discontinue pembrolizumab and duvelisib 	

Abbreviations: ALT: alanine aminotransferase; AST: aspartate transaminase; DRESS: drug reaction with eosinophilia and systemic symptoms; SJS: Stevens Johnson syndrome; TEN: toxic epidermal necrolysis; ULN: upper limit of normal.

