6.6.2. Recommended Duvelisib Dose Modifications for the Management of Duvelisib Toxicities

The dose level of duvelisib may be modified to manage duvelisib toxicities ([Table 12](#)) or overlapping toxicities in combination with pembrolizumab ([Table 10](#)).

Non-hematologic and hematologic AEs for duvelisib for non-overlapping toxicities in combination with pembrolizumab should be managed with supportive care, treatment hold, dose reduction, or discontinuation of duvelisib as described in [Table 12](#). Additional information regarding management of duvelisib toxicities can be found in the Summary of Data and Guidance to the Investigator section of the duvelisib IB.

Refer to [Table 11](#) for dose level modifications recommended for duvelisib. Subjects who have a duvelisib dose reduction due to a toxicity will not be eligible for a dose re-escalation.

Any subject who develops an unacceptable toxicity at the 15 mg BID dosage of duvelisib should discontinue the study interventions.

Duvelisib may be held up to 42 days due to toxicity. While duvelisib is being held, the subject may continue to receive pembrolizumab at the discretion of the Investigator. Doses held for > 42 days due to treatment-related toxicity will result in permanent discontinuation of duvelisib.

If duvelisib is discontinued, the subject will also discontinue pembrolizumab and proceed with their End of Treatment (EoT) Visit.

Table 11: Duvelisib Dose Level Modifications for Toxicities

Dose Level	Duvelisib
Starting Dose	25 mg BID PO
-1	15 mg BID PO ^a

Abbreviations: BID: twice daily; PO: oral.

^a Discontinue duvelisib if subject is unable to tolerate duvelisib 15 mg BID.

Table 12: Recommended Duvelisib Dose Modifications for the Management of Duvelisib Toxicities

Toxicity	Adverse Reaction Grade	Dose Modification and Recommended Management
Non-hematologic Adverse Reactions		
Infections	Grade 3 or higher infection	
 Withhold duvelisib until resolved Resume at the same or reduced dose (see Table 11)
	Clinical CMV infection or viremia (positive PCR or antigen test)	
 Withhold duvelisib until resolved Resume at the same or reduced dose (see Table 11) If duvelisib is resumed, monitor subjects for CMV reactivation (by PCR or antigen test) at least monthly
	PJP	
 For suspected PJP, withhold duvelisib until evaluated

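### Table 10 gives conflicting rules for restarting duvelisib after Grade 1 and Grade 2 diarrhea or colitis, and its reduced dose does not exist for subjects already at 15 mg BID

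*Combined protocol and SAP*

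**What the plan says.** Three rows of Table 10 in Section 6.6.1 matter here.

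- **Grade 1, refractory.** The trigger is "Grade 1 diarrhea (up to 3 stools per day over baseline) and unresponsive to antidiarrheal agents". Duvelisib is withheld, the pembrolizumab instruction is "No change in pembrolizumab dose", and an enteric acting steroid is given. The restart instruction is to resume duvelisib at a reduced dose, as set out in Table 11, once the event resolves.
- **Grade 2 diarrhea or colitis.** The action is "Withhold pembrolizumab and duvelisib", with prednisone or equivalent starting at 1 to 2 mg/kg/day and then a taper. The restart rule is "Resume in subjects with complete or partial resolution (Grades 0 to 1) after corticosteroid taper". No restart dose is given.
- **Symptomatic or Grade 3.** Both drugs are withheld. The management column names Grade 2 as well as Grade 3 colitis, and duvelisib restarts at a reduced dose on resolution.

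Section 6.6.2 adds: "Subjects who have a duvelisib dose reduction due to a toxicity will not be eligible for a dose re-escalation". Table 11 has two levels, 25 and 15 mg BID, with the footnote "Discontinue duvelisib if subject is unable to tolerate duvelisib 15 mg BID". Section 6.6.2 also ends duvelisib after a hold of more than 42 days for treatment-related toxicity, and stopping duvelisib stops pembrolizumab. Section 7.1 repeats the 42-day rule with a Medical Monitor exception.

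For the monotherapy lead-in, Table 12 puts refractory Grade 1 and Grade 2 diarrhea in one row: hold until resolved, then resume at a reduced dose.

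**The concern.** Restart rules should tell a site, for a given subject on a given day, whether to give duvelisib and at what dose. Here two rows can apply to the same subject and disagree on whether to restart, and another pair disagrees on the threshold and dose for Grade 2 colitis. For subjects at 15 mg BID, the instruction to reduce cannot be carried out at all.

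The stake is uniform conduct. Sites reading different rows would give different duvelisib doses, hold for different lengths of time and possibly discontinue different subjects. Section 2.4.1 lists diarrhea/colitis among the important identified risks of duvelisib and among the potential overlapping toxicities, so these rows are likely to be used. In Cycle 1 of Stage 1, the length of a hold can also decide whether one of the first six subjects is DLT-evaluable: without a DLT, Table 16 requires at least 75% of the scheduled duvelisib doses.

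**Working it through.** The plan states no figure on this point, so the check sets the rows side by side and follows a subject through them.

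**Step 1. Compare the three Table 10 rows.**

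| Element | Grade 1, refractory | Grade 2 diarrhea or colitis | Symptomatic or Grade 3 (also names Grade 2 colitis) |
|---|---|---|---|
| Pembrolizumab | unchanged | withheld | withheld |
| Steroid | enteric acting | 1 to 2 mg/kg/day prednisone or equivalent, then taper | enteric acting or systemic |
| Duvelisib restart threshold | event resolved | Grade 0 to 1 after taper | event resolved |
| Duvelisib restart dose | reduced | not stated | reduced |

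Between the first two columns, the Grade 1 row is stricter on the two duvelisib restart elements, and the Grade 2 row is stricter on pembrolizumab and steroids. The order is reversed on 2 of 4 elements.

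**Step 2. Size of the reduction.** The only step in Tables 6 and 11 is 25 to 15 mg BID. Daily dose: 2 × 25 = 50 mg and 2 × 15 = 30 mg. Reduction: (50 − 30) / 50 = 40%. Section 6.6.2 rules out going back up.

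**Step 3. Residual Grade 1 after Grade 2.** A subject has Grade 2 diarrhea. Both drugs are held, corticosteroids are given and tapered, and the diarrhea improves to Grade 1. The Grade 2 restart condition is met, so that row says resume. If the remaining Grade 1 diarrhea does not respond to antidiarrheals, the subject also meets the trigger of the Grade 1 refractory row. That row says withhold duvelisib until resolution and then restart at a reduced dose. Nothing in Table 10 says which row governs.

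**Step 4. Grade 2 colitis.** It is in the title of the Grade 2 row (restart at Grade 0 to 1, no dose stated). It is also in the management column of the symptomatic or Grade 3 row (restart on resolution, reduced dose). Both the threshold and the dose instruction differ.

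**Step 5. Compare with Table 12.** In the lead-in, refractory Grade 1 and refractory Grade 2 diarrhea both restart at a reduced dose after resolution. In combination, only the Grade 1 row keeps that rule for diarrhea below Grade 3 without the listed symptoms. Elsewhere Table 10 states a reduced restart dose explicitly (Grade 3 cutaneous reactions, Grade 2 pneumonitis), so the silence in the Grade 2 row cannot be filled from a general rule.

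**Step 6. Subjects at 15 mg BID.** Tables 6 and 11 end at 15 mg BID, so an instruction to resume at a reduced dose has no level to point to. Section 6.6.2 and the Table 11 footnote require stopping for unacceptable toxicity or inability to tolerate 15 mg BID. Section 7.1 leaves unacceptable toxicity to the Investigator. Whether refractory Grade 1 diarrhea that has resolved counts as either is not stated. The gap could affect many subjects: under Section 4.1, 2 or more DLTs in the first 6 subjects restarts enrollment at 15 mg BID, and Section 9.1 then evaluates the primary endpoint in subjects starting at that dose.

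**The case against.** The best case for leaving the table alone has four parts.

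- **The rows have different triggers.** At onset a subject is either Grade 1 and refractory or Grade 2, so the rows do not overlap. Different rules for different triggers are a clinical choice. The amendment history (Section 10.8.1) shows that Grade 2 was separated from Grade 1 on purpose, with alignment to prescribing information among the stated reasons. This stands for the moment of onset. It does not settle which row governs Grade 1 diarrhea left after a Grade 2 event, or Grade 2 colitis, which two rows name.
- **The Grade 2 row is not more lenient overall.** It withholds pembrolizumab and requires systemic-dose corticosteroids with a taper before any restart. This stands. A reader might infer that the milder event is handled more strictly in general; the documents support that only for restarting duvelisib.
- **Silence is not full dose.** The Grade 2 row does not say that the same dose is resumed, and Section 6.6.2 permits dose modification for overlapping toxicities. This stands: a 40% cut set against an unchanged dose would compare an instruction with a silence. The silence is itself part of what needs resolving.
- **These are recommendations.** The table and section titles say so. But Section 6.6.1 refers sites to Table 10 for managing these events, and recommendations that conflict still produce differing conduct.

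The collision in Step 3 is also narrow: it needs Grade 1 diarrhea that persists after the taper and has failed antidiarrheals, which the Grade 2 row does not itself call for.

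**Conclusion.** The concern holds for restarting duvelisib. Table 10 gives opposite instructions for residual refractory Grade 1 diarrhea after a Grade 2 event and two different restart rules for Grade 2 colitis. It also calls for a reduction that cannot be made at 15 mg BID. Where the reduced-dose rule applies at 25 mg BID, its size is a permanent 40% cut in daily dose. The consequence is inconsistent dosing and discontinuation across sites. How often it would arise is unknown, because the documents give no frequency for refractory Grade 1 diarrhea.

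Two stronger readings are not supported. A reader might infer that at 15 mg BID the Grade 1 event ends both drugs while the Grade 2 event allows restart. The stopping rules at that level rest on intolerance or Investigator-defined unacceptable toxicity and apply at any grade. The 42-day hold limit also covers Grade 2 holds, and Section 7.1 allows an exception. The documents do not say explicitly whether such subjects stop or resume. A reader might also infer a shift in ORR. One subject in 30 is 1/30 = 3.3 points, but that is only the weight of one subject; nothing shows that any confirmed response would be lost.

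The conclusion rests on reading the rows as written. No view is taken on which clinical rule is right.

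**What to change.** Reconcile the Grade 1 refractory, Grade 2, and symptomatic or Grade 3 rows of Table 10 with each other and with the refractory Grade 1-2 row of Table 12. The revised text should settle:

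1. the resolution threshold for restarting duvelisib in each row;
2. the restart dose in each row, including the Grade 2 row, which now gives none;
3. which row governs Grade 1 diarrhea remaining after a Grade 2 event;
4. which row governs Grade 2 colitis;
5. how an instruction to resume at a reduced dose is to be read with Tables 6 and 11 for subjects at 15 mg BID, including any who start at that dose.

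The sponsor decides which instruction stands in each case. The cost is wording in the dose-modification tables, by amendment or clarification memo. No new data are needed, and the sample size and analyses do not change.
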